4.9.3 Assessment of Participant Compliance with Study Procedural Intervention

Participant's compliance to the intervention will be assessed with successful compliance being completion of more than 80% of the assigned sessions. Aborted sessions will be counted as unsuccessful or incompliant sessions.

5 Study Procedures and Schedule

5.2 Study Procedures/Evaluations

5.2.1 Study Specific Procedures

- **Instrumented 10 meter walking (i-10MW)**

This test will be used to assess participants' walking ability. The use of a wearable inertial sensor allows for a quantitative measurement of the main spatio-temporal parameters (i.e. speed, stride length, cadence, stance, swing and double support phase duration)

i-10MW procedure

The experimental test will be performed in a clinical setting. The participants will be instructed to walk along a 10-meter hallway at their self-selected speed and natural gait. The inertial sensor will be attached at the lower lumbar level (centered on the L4-L5 intervertebral disc) with a semi-elastic belt. The device receives acceleration signals, which are transmitted in real time via Bluetooth to a PC.

Instrumented 2 Minute Walk Test (i-2MWT)

This test will be used to assess participants' physical endurance - with the same reliability of the 6MWT (Gijbels, 2011). The objective of this test is to walk as far as possible for 2 minutes, without running or jogging.

CONFIDENTIAL

i-2MWT procedure

Participants can slow down, stop and rest as necessary, but resume walking as soon as they are able. The experimental test will be performed in a clinical setting. The participants will be instructed to walk, at maximal effort, back and forth in 30-meter (100-ft) hallway turning around cones for 2 minutes and will be permitted to use their habitual assistive devices. The inertial sensor will be attached at the lower lumbar level (centered on the L4-L5 intervertebral disc) with a semi-elastic belt. The device acquires acceleration signals, which are transmitted in real time via Bluetooth to a PC.

Device:

Wireless inertial sensor device G-sensor (BTS Bioengineering S.p.A., ITALY).
The wearable unit includes a tri-axial accelerometer, a gyroscope, and magnetometer.

- **Instrumented Time Up and Go (i-TUG)**

This test will be used to assess participants' functional mobility. The use of inertial sensor unite introduces a quantitative approach to motion analysis.

i-TUG procedure

The experimental test will be performed in a clinical setting with the participants will be instructed to sit on a standard office chair with a back support. Following a verbal signal, participants stand up, walk straight for 3 meters at a comfortable and safe speed [Podsiadlo et al., 1991], perform a 180° turn around a cone, walk back to the chair, and perform a second 180° turn to sit down.

The inertial sensor will be attached at the lower lumbar level (positioned at the center at the L4-L5 intervertebral disc level) with a semi-elastic belt. The device acquires acceleration and angular velocity signals, which are transmitted in real time via Bluetooth to a PC.

Participants will repeat the test twice: the first trial serves mainly for familiarization, while the second is actually measured and the resulting data will be processed.

Device:

Wireless inertial sensor device G-sensor (BTS Bioengineering S.p.A., ITALY).
The wearable unit includes a tri-axial accelerometer, a gyroscope, and magnetometer.

- **Electroencephalogram (EEG) evaluation paired with cognitive testing (Optional)**

Participants may be asked to wear a miniature 3-electrode head strap device at the discretion of the study staff before and after the first and final tDCS session. The EEG measures the electrical activity in the brain and quantifies and assesses the effect of tDCS intervention. EEG signal analysis may introduce a novel approach in quantifying measurements associated with cognitive load, emotional states, stress, and pain.

During the EEG measurement period, participants will complete testing using the Cogstate Brief Battery, a validated computer-based platform{CogState, 2015 #95}{Maruff, 2013 #96}{Charvet, 2018 #462} that takes approximately 10 minutes to compute, and the Symbol Digits Modalities Test (SDMT) , a 90 second paper and pencil measure of symbol to number matching.{Smith, 1982 #82}{Charvet LE, 2014 #390}

Device:

Functional Brain Activity Sensor (fBAS™) is a sticker-size, sticker-thin, wireless sensor (medical grade accuracy) that uses three EEG electrodes (Neurosteer, LTD). fBAS device comprises of a EEG sensor and a Bluetooth transmitter. EEG recordings are collected by 3 medical grade electrodes on via a forehead patch, and the captured signals are sent via low energy Bluetooth to a PC for the real-time processing.

The EEG paired with Cognitive test assessment will be an optional measurement and will be at the study staff discretion when to perform these tests (limited time and/or limited availability of fBAS device).

- **ActiGraph Evaluation (Instrumented daily assessment of physical activity and sleep, i-DPAS)**

Actigraphy testing involves the use of a portable device called an actimeter which is worn as a wristwatch that records the participant's daily routine movements over extended periods of time (days and nights) except when he/she is bathing or swimming. An Actigraphic device is worn on the wrist and includes several types of sensors to record movement, and the absence of movement for a given

CONFIDENTIAL

continuous period of time is considered as sleeping. At the end of the test period, the data from the device is downloaded to a computer for analysis using software programs to extract a number of parameters that suggest sleep and wake cycles. The use of the wristwatch device allows quantitative measurement of the participant's daily activity (based on Vector Magnitude and number of steps taken), the intensity of physical activity and hours of sleep.

i-DPSA procedure (Optional)

The participants may be asked to wear a wristwatch sensor- depends on the availability of the device- for the entire duration of the study, from the baseline visit to the follow-up visit in which the data will be collected all throughout. The participants will be instructed to wear the wristwatch sensor each day for the entire duration of the study on the wrist of non-dominant arm (it is considered to be less intrusive especially during sleep). Participants will return the device at the follow-up visit.

Device:

Tri-axial accelerometers ActiGraph wGT3X-BT (Actigraph ,Pensacola, FL), previously validated for pwMS (Motl et al., 2009).

The monitoring of daily activity with Actigraph will be optional measurement and will be at the study staff discretion when to perform this test (limited time and/or limited availability of the ActiGraph device).

- **Static posturography Test**

This test will be used to assess participants' static balance ability. The use of static force platform unite introduces a quantitative approach to the evaluation of balance and allow to compute the positions of the centre of pressure (COP) on the ground (this is estimated as compatible with the centre of gravity at about 97%). The COP will be used to calculate the following time domain measures: velocity of the COP on the anteroposterior (AP) or mediolateral (ML) axes (COP vel), the sum of the displacements of COP on the force platform (COP path), and the 95% confidence ellipse area (COP area).

Static posturography procedure

Static posturography will be performed according to a standardized procedure as follows:

Each participant will be asked to stand barefoot on the force platform, in upright static condition, double-leg stance, and with arms resting at their sides. The position of the feet on the force-platform is standardized, their feet will be placed on two 30°-oriented footprints (inter-malleolar distance 8 cm) drawn on a paper sheet placed on the force platform. Stance conditions are tested with open eyes (OE) and closed eyes (CE). Each test will be performed 2-3 times based on the ability of each participant and lasts around 30 seconds. The closed eyes static posturography will be an optional assessment depending on the level of impairment of the participant.

Device: Wii Balance Board (Nintendo) paired via Bluetooth device with a PC. It was previously validated for healthy controls and pwMS (Park and Lee, 2014, Pau et al., 2015, Pau et al., 2017).

- **Timed 25-Foot Walk (T25-FW):** it is a clinical tool that evaluates participants for quantitative mobility and leg function performance test in a timed, 25 foot walk. The scoring for the Timed 25-Foot Walk is the average of two trials.

T25-FW procedure: the patient is directed to walk 25 feet quickly and safely as possible. Participant can use the assistive devices while doing this task.

- **Cognitive Assessment**

Brief International Cognitive Assessment in MS (BICAMS) (Benedict et al., 2016): this battery includes tests of mental processing speed and memory. Specifically, it includes the Brief Visuospatial Memory Test (BVMT), Symbol Digit Modality Test (SDMT), and Rey Auditory Verbal Learning Test (RVLT).

Cogstate Brief Battery (Maruff et al., 2009): brief, computer-administered cognitive test battery that requires approximately 10 minutes for administration and consists of four cognitive tasks that measure psychomotor function, attention, working memory and memory.

CONFIDENTIAL

- **Balance Clinical Scale**

Berg Balance Scale (Berg et al., 2005): this scale objectively determine a patient's ability (or inability) to safely balance during a series of predetermined tasks. It is a 14 item list with each item consisting of a five-point ordinal scale ranging from 0 to 4, with 0 indicating the lowest level of function and 4 the highest level of function and takes approximately 20 minutes to complete.

- Participants who are not associated with the NYU MS Care Center will need the following completed by a study physician:
 - Neurological examination
 - Medical history
 - Medication history
 - Physical examination

Otherwise, this information will be provided by their physician before their baseline visit.

- **Administration of questionnaires self-administered**

12-item MS Walking Scale (12-MSWS): Measuring the impact of MS on walking ability [Hobart et al., 2003]

9-item Fatigue Severity Scale (9-item FSS): Measuring the physical aspect of fatigue [Krupp et al., 1988]

21-item Modified form of the Fatigue Impact Scale (21-item MFIS): 9 items for physical aspects, 10 items for cognitive aspects and 2 items for psychosocial aspects [Fisk et al, 1994]

Visual Analogue Scale for fatigue (VAS- F 0-10): Measuring the perceived general fatigue on a scale from 0 mm (no fatigue) to 10 mm (extreme fatigue) [Hewlett et al., 2007]

Visual Analogue Scale for pain (VAS- P 0-10): Measuring the pain rating on a visual analogue scale from 0 mm (no pain) to 10 mm (severe, worst pain)

54 items Multiple Sclerosis Quality of Life (54-MSQOL): multidimensional health-related quality of life measure that combines both generic and MS-specific items into a single instrument

5.3 Study Schedule

5.3.1 Screening

- Obtain informed verbal consent from potential participant to discuss study and medical history
- Review medical history to determine eligibility based on inclusion/exclusion criteria.
- Review medications history to determine eligibility based on inclusion/exclusion criteria.
- Schedule study enrolment visit for participants who are eligible and available for the duration of the study.

5.3.2 Enrollment/Baseline (Visit 1)

- Obtain informed consent of potential participant verified by signature on study informed consent form
- Verify inclusion/exclusion criteria (Section 5.1)
- Obtain demographic information, medical history, medication history
- Neurology Exam/Obtain EDSS (If participant is outside of NYU)
- Assessment of weight, height, and BMI
- Baseline measure: gait assessment with instrumented 10-meter walk (i-10MW), functional mobility assessment with instrumented Time Up and GO (i-TUG), Timed 25-Foot Walk (T25-FW), instrumented 2 minute walk (i-2MW) test, balance assessment with static posturography test, administration of Berg Balance Scale, and administration of questionnaires (9-item FSS, 21-item MFIS, MSWS-12, 54-MSQOL, and VAS- F 0-10)
- Cognitive assessment using BICAMS and CogState brief battery
- Provide instructions for wearing the ActiGraph device (optional)
- First tDCS session

CONFIDENTIAL

This material is the property of the NYU School of Medicine and Langone Medical Center. Do not disclose or use except as authorized in writing by the study sponsor

Interventional Template Version: 28 APR 2017

5.3.3 Intermediate Remote Visits (Day 2 to Day 10)

- Administer the study treatment for 9 visits
(Active stimulation: 20 mins of tDCS (2.5mA) while participants will complete physical training; Sham stimulation: 20 mins of tDCS sham stimulation, no current delivery during the session, while participants will complete physical training)
- Record adverse events as reported by participant with pain ratings (VAS- P₁₋₁₀) and self-reporting and rating possible adverse events during each stimulation session
- Monitoring of perceived exertion using Borg scale. Borg scale will be administered by study technician every 5 minutes during the 20 minutes PA training
- Instructions provided to participants after the session: no concurrent physical therapy for the entire duration of the study
- Optional: Only for the first (day 1) and follow-up (day 11) may participants' be asked to wear EEG electrodes. While performing cognitive tests (CogState and the SDMT) before and after the stimulation period, participant's EEG signals will be simultaneously recorded for ten minutes.

5.3.4 Treatment End visit (within 3 days after session 10)

- Gait assessment with instrumented 10-meter walk (i-10MW), functional mobility assessment with instrumented Time Up and GO (i-TUG), Timed 25-Foot Walk (T25-FW), instrumented 2 minute walk (i-2MW) test, balance assessment with static posturography test, administration of Berg Balance Scale, and administration of questionnaires (9-item FSS, 21-item MFIS, MSWS-12, 54-MSQOL, and VAS- F 0-10)
- Cognitive assessment using BICAMS and CogState brief battery

5.3.5 Final Study Visit (within 4 ± 1 weeks from the end of treatment i.e. Session 10)

- Gait assessment with instrumented 10-meter walk (i-10MW), functional mobility with instrumented Time Up and GO (i-TUG), and balance assessment with static posturography test, administration of Berg Balance Scale, Timed 25-Foot Walk (T25-FW)
- Administration of questionnaires (9-item FSS, 21-item MFIS, MSWS-12, 54-MSQOL, and VAS- F 0-10)
- Record participant's adherence to treatment program
- Cognitive assessment using BICAMS and CogState brief battery
- Collect the ActiGraph device (Optional)

5.3.6 Withdrawal/Early Termination Visit

Subjects may withdraw from the study at any time without prejudice to their care.

6 Assessment of Safety

A data safety monitoring plan (DSMP) will be implemented to ensure safety throughout the study. The study PI and Co-I [name] will be responsible for the evaluation of safety.

There is a large body of literature indicating no known safety or tolerability risk for use of tDCS. Further, tDCS is currently being studied as an alternative to relatively higher risk treatments (such as medication) in special populations such as pregnant women and developmentally disabled children. Published studies in MS, including the work in our lab here at NYULH and Stony Brook Medicine, show tDCS to be a tolerable and safe treatment approach. [name] and team at the MS Center are MS specialists with extensive experience in the assessment of patients with MS, including cognitive capacity, and including capacity to consent for numerous clinical drug trials where there is a substantially greater potential risk posed than what are the known risks for tDCS.

EEG is also established as a safe and painless procedure, with the major side-effect only being a temporary discomfort from the gel applied on the electrode patch to improve conductivity. It poses low risks even for critically ill populations as well such that it is used as a continuous monitoring tool for patients during anesthesia

CONFIDENTIAL

This material is the property of the NYU School of Medicine and Langone Medical Center. Do not disclose or use except as authorized in writing by the study sponsor

Interventional Template Version: 28 APR 2017

and in intensive care environments (Jameson, et al. 2006). Previous literature suggests that the combined use of EEG after tDCS does not increase any risks of harm. No complications or adverse events were reported for subjects whose EEG recordings were taken after performing motor tasks paired with tDCS stimulation (Polania, et al. 2012; Notturno, et al. 2013; Greecco, et al. 2014).

Actigraphy is also a safe tool that is increasingly utilized in clinical research. In a number of clinical trials, it has been used to monitor patient's responses to new treatments, and no safety concerns were raised when worn on vulnerable populations such as nursing home patients with advanced dementia, (Erdal, et al. 2018) and hospitalized elderly with high risk of delirium (Jaiswal, et al. 2018). Therefore, taken together, we do not believe that neither the simultaneous use of tDCS and EEG nor use of ActiGraph represents a situation where an independent party would be needed.

Weekly meetings between the PI, co-investigators, and study coordinators will review the clinical course and assessments of each subject. There are no pre-defined rules for stopping the study.

DSMP meetings will occur after the completion of every 10 study participants (all study procedures completed). Information to be reviewed at DSMP meetings will include adverse event rates and protocol compliance to ensure that the study is being conducted safely and is in line with the current safety expectations associated with tDCS (i.e. no serious adverse effects are associated with tDCS).

Reports will be submitted at the annual review unless a change in the risk/benefit ratio has been identified from the safety and adverse event data (in which case a report will be promptly submitted to the IRB).

Non-Significant Risk Device Justification:

As described above, tDCS poses low risks to participants and our protocol is well-tolerated. To our knowledge, hundreds of tDCS studies in the US have all been designated Non-Significant-Risk (NSR) level (devices that are not: intended as an implant with potential for serious risk to health, safety, or welfare of subject; purported or represented to be for use in supporting or sustaining human life with a potential for serious risks; for use of substantial importance in diagnosing curing, mitigating, treating disease or otherwise preventing impairment of human health with potential for significant risk; otherwise presents significant risk to the health, safety, or welfare of a subject). For these reasons, the Soterix Mini CT, as used in this study, also qualifies as a NSR device.

While tDCS remains an investigational technique (simply because no company has applied to the FDA for approval to market tDCS for any given indication), tDCS is a broadly reproduced and tested technique that is considered effective in modulating brain excitability in a manner that may support learning and with adverse events (different than sham) limited to tingling, itching, and redness that dispel after stimulation stops. In a prior study of use in a vulnerable population (developmentally disabled children), the FDA issued a NSR for tDCS device (see attached letter). The letter provided as an example of the FDA's designation of tDCS devices as abbreviated IDE. Because of its prior designation of tDCS devices as abbreviated IDE, trials do not typically seek further declaration. In the letter provided, [name] specifically sought FDA review of the trial due to the use of tDCS in a vulnerable population (developmentally disabled children).

To date, hundreds of trials have been designated as non-significant risk by IRB review which provides its abbreviated IDE status. Results of completed trials, including our own work in MS using this protocol, have supported the risk designation provided by IRBs. The Stony Brook Medicine IRB confirmed the NSR and abbreviated IDE status of tDCS for our study and others at the institution. We have learned that the NYU IRB has also confirmed tDCS devices (including those manufactured by Soterix) as abbreviated IDE for current ongoing studies at this institution. The safety of this technique has been addressed and tested by multiple researchers (e.g., Hummel, et al. 117; Fregni, et. al. 19, 118; Nitsche, et al. 13, 24, 119; Priori, et al. 120) who have concluded that tDCS, as applied in a manner similar to our proposed protocol, induces only temporary mood, cognitive / motor effects, and no negative side effects. For example, researchers at the National Institute of Neurological Disorders and Stroke (NINDS), Iyer et al. 19 conducted a safety study on tDCS, investigating 20-minute sessions of 1 mA and 2 mA current stimulation with healthy controls (n=103). No negative effects were identified. Nitsche and colleagues found no measurable structural changes in brain tissue due to tDCS

CONFIDENTIAL

This material is the property of the NYU School of Medicine and Langone Medical Center. Do not disclose or use except as authorized in writing by the study sponsor

Interventional Template Version: 28 APR 2017

121. In a meta-analysis of over 200 tDCS studies conducted from 1998 to 2010, 56% of studies mentioned adverse events, which were generally minor.

The most commonly reported side effects included itching, tingling, headache, burning sensation and discomfort limited to the scalp site where the tDCS electrodes were applied. To date, there have been no reports of seizures induced by tDCS. Importantly this is the case in normal volunteers, but also in different populations of patients, including patients with disorders where there might be an increased risk of seizures (e.g. Alzheimer's disease, recent stroke, epilepsy). A study from NYU on the use of tDCS in patients with epilepsy¹²² encountered no increase in complications of tDCS in the patients as compared with controls. Specifically, there were no instances of seizures induced by tDCS.

Non-invasive EEG is also considered to be a tolerable and safe routine procedure. As of today, it is designated minimal risk by IRB Review (a procedure in which the probability and the magnitude of harm or discomfort caused are not greater than those encountered in daily life). The fBASfor use intended in this study also qualifies as a minimal risk device.

Cubii Pro Elliptical complies with FCC part 15 FCC Rules. This equipment is minimal risk because it is a non-invasive elliptical machine widely available for at-home workout composed of pedal bike cycle motion with adjustable resistance. Participants will be informed of all safety precautions:1) Use Cubii Pro only while sitting; 2) Use Cubii Pro indoors on a level surface; 3) Cubii Pro only by holding the handle; 4) For ensure maximum grip with the pedals, we recommended wearing soft sole shoes and straps.

ActiGraph also qualifies as a minimal risk by IRB because it is a non-invasive, physical sensor or watch that is only applied to the surface of the body. To date, there are numerous actigraphy testing devices that have been cleared for 510(k) process, and specifically, ActiGraph wGT3X-BT, the device that is used for this study, has already been approved as a Class II medical device by the FDA. More information are provided in the User Manual attached.

The static posturography test performed with force platform is not associated with any risks. The procedure of the posturography test is considered to be tolerable and safe procedure routine.

Participants in all groups may find the questionnaires time consuming and potentially bothersome. Neuropsychological testing and the physical activity sessions may, in some individuals, be stressful or anxiety producing.

There is a small risk of loss of confidentiality. Participants will be assigned a study ID and their name will not be used on any of the information collected. The results of these data collected may be used for publication but will not include the participants' names. Data will be stored in an IRB-compliant manner that is consistent with MCIT's policies.

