3.4.2 Secondary Study Endpoints

- The feasibility of delivering at-home supervised PA paired with tDCS will be assessed using the number of completed sessions at-home. It will be considered as “feasible” when participant complete successfully at least 80% of the total at-home sessions
- Comparisons between the active and sham conditions at baseline and at the end of the study by assessing the changes in gait spatial-temporal parameters (stance, swing and double support phase; cadence; step width) and functional mobility parameters objectively assessed using wearable inertial sensors
- Comparisons between the active and sham conditions at baseline and participation end conditions by assessing the changes in scores of 9-item FSS (physical aspect of fatigue) and 21-item MFIS (physical 9 items, cognitive 10 items, psychosocial 2 items), MSWS-12 (subjective measures of impact for walking ability and related pathology), and MSQOL-54 (36 items for generic health-related quality of life measures and 18 items for MS-specific measures).
- Comparisons between the active and sham conditions at baseline and participation end conditions by assessing the changes in scores of VAS- F₀₋₁₀ (to assess the perceived general fatigue)
- Review of experiences of minor adverse events and pain ratings. In particular, participants will have to report and rate any adverse events. Pain ratings will be measured, using a VAS- P₀₋₁₀ (rating 1 for minimal to 10 for most severe), before and after each session (any experience of pain or other adverse event above an intensity rating of 7 will result in study discontinuation)
- Comparisons between the active and sham conditions at pre and post tDCS-PA session by assessing the changes in the performance of the cognitive tests and EEG signal changes during the time of testing
- Comparisons between the active and sham conditions at baseline and participation end conditions by monitoring the changes in level of daily physical activity and amount of sleep as measured by ActiGraph
- Comparisons between the active and sham conditions at baseline and participation end conditions by monitoring the changes in sway parameters as objectively measured by the instrumented Posturography test and by monitoring changes in total score Berg Balance Scale.
- Change in processing speed between baseline and immediately after the treatment end to assess improvement in cognitive function as indirect effect of aerobic PA.

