6.4 Reporting Procedures – Notifying the IRB

6.4.1 Adverse Event Reporting

Adverse event rates will be calculated and reviewed at DSMP meetings. Adverse event rates will be reported to the IRB as described previously. Should adverse event rates exceed the normal rates observed in the literature, the study PI will place the study on hold and review the safety of the study.

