6.6 Safety Oversight

It is the responsibility of the Principal Investigator to oversee the safety of the study at his/her site. This safety monitoring will include careful assessment and appropriate reporting of adverse events as noted above, as well as the construction and implementation of a site data and safety-monitoring plan. Medical monitoring will include a regular assessment of the number and type of serious adverse events by Co-I [name].

Safety and tolerance of study protocols will be assessed via safety reports after every ten participants that complete the study. Signed memos including the details of the reports will be submitted to the IRB in a timely fashion.

7 Statistical Considerations

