Interventional Template Version: 28 APR 2017

16 Schedule of Events

Activity	Screening	Baseline	tDCS +activity sessions	Study visit 11/ Treatment End Visit (approx. 3 days after end treatment)	Follow-up visit (Optional) [4 ±1 week post- Study Visit 10]
Study team procedures					
Consent	X				
Medical History	X				
Physical Exam	X				
Height		X			
Weight		X			
Neurological examination	X				
Randomization	X				
tDCS+ PA treatment		X	X	X	
Participant device compliance check				X	
Assessment of perceived exertion (Borg Scale)			X		
Instrumented evaluation of mobility					
i-10MW test		X		X	X
Timed 25-Foot Walk (T25-FW)		X		X	X
i-TUG test		X		X	X
Static Posturography Test	X	X		X	X
EEG assessment (Optional)		X		X	
i-2MW test		X		X	X
i-DPAS (Optional)		X	X	X	X
Questionnaires, Clinical Scale and Cognitive Assessment					
BICAMS		X		X	X
Cogstate Brief Battery		X		X	X
Berg Balance Scale		X		X	X
FSS		X	X	X	X
54-MSQOL		X			X
12-MSWS		X	X	X	X
21- MFIS		X	X	X	X
VAS- F 0-10		X	X	X	X
VAS- P 0-10		X	X	X	
Reported Adverse Events		X	X	X	

CONFIDENTIAL

CONFIDENTIAL

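### Scheduled adverse event rate reviews are counted in completers, so participants stopped for harm (like any other dropout) make them later and fewer; the loss is about one review at the planned 10% dropout

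*Combined protocol and SAP*

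**What the plan says.** Section 6 (Assessment of Safety) sets the meeting interval: "DSMP meetings will occur after the completion of every 10 study participants (all study procedures completed". On content it says: "Information to be reviewed at DSMP meetings will include adverse event rates and protocol compliance". Section 6.6 (Safety Oversight) repeats the trigger: "Safety and tolerance of study protocols will be assessed via safety reports after every ten participants that complete the study".

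Section 6.4.1 states: "Adverse event rates will be calculated and reviewed at DSMP meetings". It then gives a study-level consequence: "Should adverse event rates exceed the normal rates observed in the literature, the study PI will place the study on hold".

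Two sections describe how an adverse event can end participation. Section 3.4.2 says that "any experience of pain or other adverse event above an intensity rating of 7 will result in study discontinuation", and Section 4.6.1 lets the investigator end participation because of an adverse event. Section 5.3.6 carries the heading of an early termination visit but lists no procedures under it.

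Section 4.5 stops recruitment at about 80 and allows for 10% dropout, leaving 72 evaluable. It does not mention replacement. The last visit appears in Section 16 as "Follow-up visit (Optional) [4 ±1 week post- Study Visit 10", and the visit table in Section 4.4 also marks it optional.

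**The concern.** A count that drives safety review should not slow down when tolerability is worse than expected. Here the participants whose experience signals a problem, those stopped for pain or an adverse event, are the ones who do not count towards the next ten. Two sections use the same trigger, so it reads as the intended design and not as a slip.

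What is at stake is the timing of the one scheduled occasion on which adverse event rates are said to be calculated. The comparison with published rates that can lead to a hold needs those rates. The protocol has no pre-defined stopping rules (Sections 6 and 6.5), and safety is evaluated by the investigator and a co-investigator, so the periodic rate review carries more weight than it otherwise would.

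Separately, staff cannot tell from the text when a meeting is due. If the last procedure is optional, a participant who skips it may or may not have completed everything.

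**Working it through.** **Inputs from the protocol**
- About 80 enrolled, 10% dropout, 72 evaluable, no replacement stated (Section 4.5).
- One review per 10 completers (Sections 6 and 6.6).
- Ten sessions over two weeks, with missed sessions made up in a third week (Section 4.4).
- Treatment-end visit within 3 days of session 10 (Section 5.3.4); final visit 4 ± 1 weeks after session 10 (Section 5.3.5).

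**Assumptions**
- Dropout is equated with non-completion.
- Non-completion of 20% and 30% is used only to show a range.
- For step 4, 1 to 2 participants start per week.

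**Step 1. Reproduce the protocol's figure.** 80 × (1 − 0.10) = 72, as stated.

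**Step 2. Reviews under the completer trigger.** With non-completion q:
- completers = 80(1 − q)
- reviews = completers ÷ 10, rounded down
- expected entrants needed for ten completers = 10 ÷ (1 − q)
- chance that the first ten entrants do not suffice = 1 − (1 − q)^10

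| q | Completers | Reviews | Entrants per review | Chance that first review needs more than 10 entrants |
|---|---|---|---|---|
| 0 | 80 | 8 | 10.0 | 0% |
| 10% (planned) | 72 | 7 | 11.1 | 65% |
| 20% (assumed) | 64 | 6 | 12.5 | 89% |
| 30% (assumed) | 56 | 5 | 14.3 | 97% |

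A count based on participants treated would give 80 ÷ 10 = 8 reviews in every row. At 10%, the seventh review falls at the 70th completer. The last 72 − 70 = 2 completers, and anyone stopped after that point, have no scheduled review.

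**Step 3. Time from first session to completion.**
- If completion means the treatment-end visit: 2 + 3/7 = 2.4 weeks to 3 + 3/7 = 3.4 weeks.
- If it means the follow-up visit: 2 + 3 = 5 weeks to 3 + 5 = 8 weeks.

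**Step 4. Participants started before the first review, at 10% dropout.** Started = 11.1 + lag × starts per week.
- Treatment-end reading: 11.1 + 2.4 × 1 = 13.5 to 11.1 + 3.4 × 2 = 17.9, about 18.
- Follow-up reading: 11.1 + 5 × 1 = 16.1 to 11.1 + 8 × 2 = 27.1.
- Follow-up reading with no dropout: 10 + 5 = 15 to 10 + 16 = 26.

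Dropout adds only 11.1 − 10 = 1.1 participants. The rest of the excess over ten comes from the lag and the assumed enrolment rate.

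**The case against.** The strongest reply is that much of the safety monitoring does not wait for completers:
- weekly meetings review each subject's course (Section 6);
- the co-investigator regularly assesses the number and type of serious events (Section 6.6);
- the study can be suspended for reasonable cause on an open-ended list of grounds (Section 4.7);
- related serious events go to the IRB within 24 hours, and unanticipated problems within 24 hours or five business days (Sections 6.4.2 and 6.4.3);
- a changed risk/benefit ratio is reported promptly (Section 6).

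This stands. A cluster of discontinuations should be seen at a weekly meeting. It does not remove the point, because none of these provisions is assigned the adverse event rate review, and several cover only serious or unanticipated events.

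The second reply concerns size. The protocol plans 10% dropout from all causes, and Section 2.2.1 reports tolerability and feasibility above 99% over more than 2000 sessions in the group's earlier tDCS work. This also stands: the higher rates in the table are not forecasts.

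Third, Section 6.6 mentions a site data and safety-monitoring plan, and Section 4.6.1 refers to separately uploaded stop criteria. Neither is in the document reviewed, and either could define completion.

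Four stronger readings are tempting but unsupported:
- *Rates are calculated only at DSMP meetings, so a hold can arise nowhere else.* Section 6.4.1 does not say only, and its hold sentence is not confined to those meetings.
- *Any increase in harm slows the reviews.* Only events that end participation do so. Itching or tingling that a participant tolerates leaves the count unchanged, and dropout for other reasons slows it equally.
- *Events in discontinued participants are left out of the rates.* Nothing says so. The defect lies in when and how often the rates are reviewed.
- *The completer rule leaves 16 to 27 participants, 20% to 34% of 80, exposed before the first review.* Step 4 shows that this rests on an assumed enrolment rate and the longest reading of completion.

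**Conclusion.** The point holds for the scheduled aggregate reviews. As written, the DSMP meetings and safety reports come later and are fewer when participants stop early, including those stopped for harm. At the protocol's own 10% dropout the loss is one review (7 instead of 8), with about 11 entrants per review instead of 10. It grows to 6 reviews at an assumed 20% and 5 at an assumed 30%. These figures assume that every dropout fails to complete and is not replaced.

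The optional 4-week visit leaves the trigger date uncertain at any dropout rate: the time to completion is 2.4 to 3.4 weeks on one reading and 5 to 8 weeks on the other. Safety is not unreviewed between meetings. The defect is modest in size, but it works in the wrong direction for a safety trigger and is cheap to correct.

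**What to change.** In Sections 6 and 6.6, trigger the meeting and the report each time 10 more participants have received at least one stimulation session (10, 20, and so on to 80). State that each review covers cumulative adverse events in all treated participants, including those discontinued. Add a final review after the last participant's last contact.

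A smaller edit would keep the present structure but count everyone who has completed or ended participation for any reason. That version must also say whether the optional 4-week visit is needed for completion.

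The cost is wording in two sections. The first-session trigger gives eight counted reviews at any dropout rate, one more than the 7 expected at 10%, plus the final review. Its small downside is that the most recent participants have had only part of their ten sessions at each cut; cumulative review picks up the remainder at the next meeting. Neither version changes a dose, a stopping criterion or any rule for managing participants.
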